# 10. STATISTICAL CONSIDERATIONS

## 10.1. Sample size determination

#### 10.1.1. Hypotheses related to primary and secondary objectives

For the primary safety objective no statistical hypotheses are applicable.

Two statistical hypotheses will be tested for the secondary efficacy objective.

- 1. Null Hypothesis : Hazard Ratio (HR) ≥1 after the second vaccination Alternative Hypothesis: HR <1
- 2. Null Hypothesis : Hazard Ratio (HR) ≥1 after the first vaccination Alternative Hypothesis: HR <1

If the first hypothesis is statistically significant, also the second hypothesis will be tested in a sequential procedure. In case the first hypothesis is not significant no conclusions will be taken with respect to the second hypothesis. Both hypotheses will be tested using the log rank test.

For the first hypothesis referring to the key efficacy endpoint two sequential analyses will be done following a Group Sequential Design using the O'Brien-Fleming spending function (with 48% and 100% of the total planned events). *(Amended 6 October 2022)* 

At the interim analysis the first hypothesis will be tested spending 1.61% alpha and 8.83% beta (this means a power equal to about 91%). At the final analysis the alpha will be 5.89% and the beta 11.17% (this means a power equal to about 89%). Overall after two sequential analyses the cumulative alpha will be 7.5% and the cumulative beta 20% (or power equal to 80%).

The assumptions to test the first hypothesis on the HR after the second vaccination are:

- to observe an HR (hazard ratio) equal or below to 0.39
- a true incidence rate for the SSTI equal to 0.07 (starting to count the events two weeks after the second dose)
- time to event follows an exponential distribution.

The second hypothesis of the secondary vaccine efficacy objective will be tested for all the events occurring after the first vaccination, with one-sided alpha equal to 5.89% and power 89% (both adjusted error values will be retrieved from the second group sequential test performed on the first hypothesis).

The following assumptions are made to test the hypothesis on the HR after the first dose of vaccine/placebo:

- to observe an HR below 0.43
- a true incidence rate equal to 0.12 (starting to count the events two weeks after the first dose)
- time to event follows an exponential distribution

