The upper limit assumed for the HR equal to 0.43 allows to test the second hypothesis with alpha equal to 5,89% and power equal to 89%, assuming the incidence rate equal to 0.12, with the planned sample size for the first hypothesis (about 600 subjects).

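### The incidences 0.07 and 0.12 cannot both hold under the stated exponential model; with any single exponential, hypothesis 2 has about 80% power at the 27-event analysis, not 89%

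*Protocol*

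**What the plan says.** Protocol 10.1.1 gives each efficacy hypothesis its own list of assumptions.

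- Hypothesis 1 (after dose 2): "to observe an HR (hazard ratio) equal or below to 0.39" and "a true incidence rate for the SSTI equal to 0.07 (starting to count the events two weeks after the second dose").
- Hypothesis 2 (after dose 1): "to observe an HR below 0.43" and "a true incidence rate equal to 0.12 (starting to count the events two weeks after the first dose").
- Both lists end with the same model: "time to event follows an exponential distribution".

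Hypothesis 2 is to be tested "with one-sided alpha equal to 5.89% and power 89"%. The closing paragraph of 10.1.1 ties that power to its inputs: "assuming the incidence rate equal to 0.12, with the planned sample size for the first hypothesis (about 600 subjects"). Neither incidence has a time unit or an arm, and no dropout rate is given.

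The sample size is open. Protocol 10.1.2 continues enrolment until the planned number of events for hypothesis 1 is reached. SAP 7.1 sets that number at 27 events after the second dose, draws the efficacy conclusions there, and excludes later data from those conclusions. SAP 7.2 tests the second endpoint at the final analysis, once the first null hypothesis is rejected.

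**The concern.** The hypothesis 2 window, Day 15 to Day 426 (411 days), contains the hypothesis 1 window, Day 75 to Day 426 (351 days), plus 60 earlier days. An exponential from Day 15 is memoryless, so it also fixes the hazard after Day 75. The footnote to Figure 12 keeps subjects with a case before dose 2 in the hypothesis 1 count, so prior cases do not thin out the later window. Adding 60 days to 351 cannot raise the incidence from 0.07 to 0.12 at a constant hazard. If the figures are rates per person-time, a constant hazard requires them to be equal.

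At stake is the stated power of a hypothesis under an objective labelled confirmatory. Hypothesis 2 has no event target of its own. Its event count is whatever has accrued when hypothesis 1 reaches 27.

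**Working it through.** **Inputs.** From Protocol 10.1.1: HR 0.39 and 0.07 (hypothesis 1); HR 0.43, 0.12 and one-sided alpha 0.0589 (hypothesis 2). From SAP 7.1: 27 events. Allocation is taken as 1:1, ignoring the 3:1 ratio in the first 40 or so subjects. Incidences are read as placebo cumulative risks unless noted.

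**Formulas.** Expected events = N/2 × [p + 1 − (1 − p)^HR]. With z = 1.564 for alpha 0.0589, Schoenfeld power is Φ(|ln HR|·√(E/4) − z) and Freedman power is Φ(√E·(1 − HR)/(1 + HR) − z).

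**1. The plan's 89%.** It matches 1 minus the final-stage beta of 11.17%. It also reproduces at N = 600 with 0.12 as a yearly rate over one year: 300 × (2 − e^−0.12 − e^−0.0516) = 49.0 events, Freedman 89.0%. Other conventions differ. With 0.12 as a cumulative risk at N = 600 there are 52.0 events (Freedman 90.5%, Schoenfeld 93.1%). Schoenfeld gives 88.8% at N = 500.

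**2. Consistency.** −ln(0.93) = 0.0726 over 351 days; −ln(0.88) = 0.1278 over 411 days.
- 0.07 scaled to 411 days: 1 − exp(−0.0726 × 411/351) = 0.0815.
- 0.12 scaled to 351 days: 1 − exp(−0.1278 × 351/411) = 0.103.
- Ratio of the two implied hazards: (0.1278/411)/(0.0726/351) = 1.50.

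Reading 0.07 as pooled over both arms does not help: 27/0.07 is about 386 subjects, against the planned 500 to 600.

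**3. Events for hypothesis 2 at 27 hypothesis 1 events, single exponential, all subjects fully followed.**
- 0.07 right: N = 27 / {½[0.07 + 1 − 0.93^0.39]} = 552. Events = 276 × [0.0815 + 1 − 0.9185^0.43] = 32.4. Power 80% (Schoenfeld), 76% (Freedman).
- 0.12 right: N = 27 / {½[0.1034 + 1 − 0.8966^0.39]} = 372. Events = 186 × [0.12 + 1 − 0.88^0.43] = 32.3. Power is the same.

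The incidence drops out because, at a constant hazard, the event ratio is close to the ratio of follow-up times: 27 × 411/351 = 31.6.

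**4. With staggered entry.** Assume uniform accrual of 0.3 to 1 subject per day, no dropout, and a cut at the 27th event. A subject who has been in the study u days contributes min(max(u − 74, 0), 351) days to hypothesis 1 and min(max(u − 14, 0), 411) days to hypothesis 2. Integrating over entry times gives about 33 to 35 hypothesis 2 events under either hazard. Accrual of up to 60 per month gives up to 36. Over 32 to 36 events, power is 80 to 83% (Schoenfeld) or 76 to 80% (Freedman).

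**5. What 89% needs.** With 1.564 + 1.227 = 2.791: Schoenfeld 4 × 2.791² / (ln 0.43)² = 44 events; Freedman 2.791² × (1.43/0.57)² = 49. With 32 to 36 events, the HR detectable at 89% power is exp(−2 × 2.791/√E) = 0.37 to 0.39 (Schoenfeld).

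**6. Keeping both 0.07 and 0.12.** The first 60 days then carry a cumulative hazard of 0.1278 − 0.0726 = 0.0553, a risk of 5.4%.
- Early to late hazard ratio: (0.0553/60)/(0.0726/351) = 4.5.
- Early share of the placebo cumulative hazard: 0.0553/0.1278 = 43%.
- Implied HR in Day 15 to 75: (0.43 × 0.1278 − 0.39 × 0.0726)/0.0553 = 0.48.

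At 552 to 600 subjects there are 48 to 52 events and simulated log-rank power is 89 to 91% (Schoenfeld 91 to 93%).

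**The case against.** The strongest reply is that log-rank power depends on the number of events, not on exponential shape. If 0.07 and 0.12 are separate empirical estimates for each window, and exponential is only a working approximation listed under each hypothesis, front-loaded recurrence makes them compatible and the 89% survives. Protocol 5.1 bases the efficacy assumptions on a retrospective review of three hospital databases, so this is plausible. The documents neither confirm nor exclude it. That part stands, and it is why front-loading is one of the two remedies. It does not rescue the text as written, which states an exponential and never mentions the early-period effect.

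A second reply is that if 0.12 is right and 0.07 too low, hypothesis 2 power stands and hypothesis 1 simply accrues faster. That holds at a fixed 600 subjects. It fails here because enrolment and the analysis stop at 27 events, reached with about 372 fully followed subjects under that hazard.

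Third, the event-driven rule partly protects hypothesis 2, because the windows are nested. This stands. A reader might infer a larger loss from the case of 500 subjects at 0.0815: 29 events and power of 76% (Schoenfeld) or 72% (Freedman). The design is not expected to stop there. With 0.07 and HR 0.39, 500 subjects give only 24.5 hypothesis 1 events, so enrolment would continue.

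**Conclusion.** The three statements 0.07, 0.12 and exponential cannot all be true. Under any single exponential, hypothesis 2 has about 80% power at HR 0.43, against a stated 89%. The shortfall is about 6 to 9 points by Schoenfeld and 9 to 13 by Freedman. The stated power is attainable under a front-loaded hazard, with an early-period HR of about 0.48 that the plan does not disclose.

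This rests on placebo cumulative risks, no dropout, the assumed accrual, and a cut at the 27th event as SAP 7.1 describes. It concerns the final analysis, not a stop for efficacy at the interim.

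A reader might also infer that 0.12 contradicts the first hypothesis itself, or that error control suffers. The documents do not support either. The first hypothesis is HR ≥ 1 against HR < 1, and 0.12 conflicts only with its incidence assumption under a common exponential. Type I error, the 27-event target and the power of hypothesis 1 do not depend on it.

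**What to change.** In Protocol 10.1.1, state the time unit, arm and window of each incidence, and use one recurrence model for both hypotheses. Two routes are open:

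- Keep the single exponential. Restate hypothesis 2 power as about 80% at HR 0.43, or restate the HR detectable with 89% power (about 0.37 to 0.39 by Schoenfeld). Name the formula used.
- Replace the exponential with a piecewise exponential consistent with 0.07 and 0.12 (about 5.4% in Day 15 to 75, then 7%). Keep the power at about 89% and disclose the implied early-period HR of about 0.48.

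The source data behind the two incidences should decide between them. The cost is one recalculation, a few sentences, and possibly a less favourable stated power. Enrolment rules, the event target and the testing order stay as they are.

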## 10.1.2. Sample size calculation

The incidence rates of *S. aureus* SSTI (index cases and recurrences) at the selected study centre(s) are difficult to predict. For this reason, the study is designed as an event driven trial and includes **CO**. After the dose-escalation safety lead-in epoch and the PoP staggered enrolment step of PoP vaccination epoch are concluded and no safety issues are found, enrolment will continue with a randomisation of 1:1 ratio either to the *S. aureus* candidate vaccine or to the placebo group. It is estimated that approximately 500 to 600 subjects will be needed to achieve the **CO** 

The key objective of clinical efficacy will be measured counting culture confirmed cases of recurrent *S. aureus* SSTIs occurring from 14 days after the second dose up to 12 months after the second dose. Before the second dose has elicited a proper response (i.e. from Day 61 to Day 75) subjects will be also monitored for SSTI.

The event driven design includes **CCL** (culture confirmed *S. aureus* SSTI recurrences) overall after the second dose to test the null hypothesis of no efficacy assuming an HR equal to 0.39 from Day 75 (14 days after the second vaccination) up to 12 months after the second vaccination.

The study sample size is not fixed and the enrolment will proceed until reaching the planned number of events necessary to evaluate the first statistical hypothesis of no efficacy (HR $\geq$ 1) with an overall power equal to 80% and an overall one-sided alpha equal to 7.5%.

A group sequential design with the O'Brien Fleming spending function is applied to the first hypothesis after the second vaccination, CCL

After the final analysis for the first hypothesis a sequential procedure will be used in order to control the overall type I error for the efficacy objective: starting from the first hypothesis on the efficacy after the second dose, the second hypothesis on the efficacy after the first dose will be tested only if the efficacy after two doses will be demonstrated.

# Figure 12 Sequence for evaluating both efficacy objectives in order to control the overall type I error below 7.5% (one-sided) and the power equal to 80%

\*All subjects who experience an SSTI recurrence at least two weeks after the second dose. If a subject experiences an event after the first and before the second dose the case will be not considered as first event after the second dose. If a subject experiences an event after the first and another after the second dose, only the case after the second dose will be considered as first event after the second dose.

\*\*The adjusted alpha for this hypothesis can only be given at the time of analysis as the adjustment is dependent on the alpha spent at the interim analysis. A more detailed decision tree will be given in the statistical analysis plan. \*\*\*All subjects who experience an SSTI recurrence at least two weeks after the first dose.

# 10.2. Populations for analyses

| Analysis Set                         | Description   |
|--------------------------------------|---|
| Screened                             | All subjects who were screened for eligibility  |
| Enrolled                             | All subjects who entered the study (who were randomized or received study intervention or underwent a post-screening study procedure). The allocation in a group will be done in function of the randomized intervention; non-randomized subjects will be part of a "Non randomized" group. Note: screening failures (who never passed screening even if rescreened) and subjects screened but never enrolled into the study (met eligibility but ultimately not enrolled) are excluded from the Enrolled analysis set as they did not enter the study. |
| Exposed                              | All subjects who received at least 1 dose of the study treatment. The allocation in a group is done in function of the administered treatment.  |
| Full Analysis Set (FAS)              | All subjects who received at least 1 dose of the study treatment and have post-
vaccination efficacy/ immunogenicity data  |
| Modified Full Analysis Set
(mFAS) | All subjects who received full study treatment course to which they are randomised and have post-vaccination efficacy/immunogenicity data   |
| Per-Protocol (PP)                    | All subjects who received full study treatment course to which they are randomised
and have post-vaccination data (mFAS) minus subjects with protocol deviations
that lead to exclusion from PP   |
| Unsolicited Safety                   | All subjects who received at least 1 dose of the study treatment (Exposed Set) that report unsolicited AEs/report not having unsolicited Aes  |
| Solicited Safety                     | All subjects who received at least 1 dose of the study treatment (Exposed Set) who have solicited safety data in the period beginning 30 minutes after vaccination until 7 days after vaccination.  |
| Solicited Safety 30m                 | All subjects who received at least 1 dose of the study treatment (Exposed Set) who have solicited safety data during a period of 30 minutes after the vaccination.  |
| Overall Safety Set                   | All subjects who received at least 1 dose of the study treatment (Exposed Set) who have solicited safety data including 30 minutes data and during a period of 7 days from the vaccination and/or report unsolicited Aes/report not having unsolicited Aes  |

For purposes of analysis, the following analysis sets are defined:

# 10.3. Statistical analyses

#### 10.3.1. Subjects disposition

Number of screened, enrolled, vaccinated (at least 1 vaccination, full vaccination course) subjects, included in each group or in total for a given age category or for all age categories will be described. These might be additionally broken down by site.

#### 10.3.2. Demography and baseline characteristics analyses

Demographic characteristics (age at first study vaccination in years, gender, race and ethnicity), SSTIs history (PoP only), will be summarised by overall and vaccine groups using descriptive statistics:

- Frequency tables will be generated for categorical variables such as centre.
- Mean, standard deviation, median, minimum and maximum will be provided for continuous data such as age, height, weight and body mass index (BMI).

Withdrawal status will be summarized by group using descriptive statistics:

- The numbers of withdrawn subjects will be tabulated according to the reason for withdrawal
- The number of subjects enrolled into the study as well as the number of subjects excluded from the per-protocol set (PPS) and mFAS will be tabulated.

#### 10.3.3. Efficacy analyses

The primary efficacy analysis will be based on the mFAS. A supplementary analysis may be based on the PPS.

#### 10.3.3.1. Case accountability:

Rules for SSTI cases:

- All cases of SSTI will be reported, including multiple cases in the same subject.
- The start date of a case is the date of the visit during which the diagnosis is done by a treating physician or equivalent licensed medical professional or based on medical records review by a study physician.
- A new SSTI episode may be assessed by a study physician at site for any SSTI visit occurring after the clinical resolution of the previous SSTI and, if it does not represent a persistence of the previous episode as per medical judgement, it can be considered a new episode.

| Endpoint     | Statistical Analysis Methods  |
|--------------|---|
| Kev          | The analysis of efficacy will be based on the occurrence of the first case of SSTI anytime from 15    |
| secondary    | Days after the administration of the second dose of the study vaccine up to 12 months. All            |
|              | subjects from the mFAS will contribute to the comparison between the treatment and the placebo        |
|              | groups.   |
|              | Time to occurrence of key secondary endpoint during the defined efficacy follow-up period will be     |
|              | compared between groups by calculating the respective Hazard ratio (methods will be detailed in       |
|              | the SAP).   |
|              | Vaccine (VE) will be defined as 1 minus the hazard ratio times 100:                                   |
|              | VE = (1 – hazard ratio) x 100   |
|              | Censoring will occur at the time of the last scheduled or medically attended visit without the        |
|              | occurrence of SSTI cases before the end of follow-up. Subjects who will complete the follow-up        |
|              | without events will be censored at 1 year.  |
|              | In order to check the statistical significance, 1-sided P-value for the log rank test will be         |
|              | calculated. 1-sided nominal type I error will be 1.61% at the interim analysis and 5.89% at the final |
|              | analysis. The objective will be met if the 1-sided P-value calculated for the null hypothesis H0 =    |
|              | [occurrence SSTI VE =0%] is lower than defined 1-sided alpha level.                                   |
| Co-secondary | The co- secondary endpoint will be analysed only if the statistical significance is demonstrated for  |
| _            | the key secondary endpoint.   |
|              | For this analysis, the FAS will account for the first case of SSTI anytime from 15 Days after the     |
|              | administration of the first dose of the study vaccine up to 14 months.                                |
|              | Time to occurrence of the co- secondary endpoint during the defined efficacy follow-up period will    |
|              | be compared between groups by calculating the respective Hazard ratio (methods will be detailed       |
|              | in the SAP).  |

#### CONFIDENTIAL

208833 (STAPH AUREUS BIOCONJ-001 STG) Protocol Amendment 6 Final

| Endpoint | Statistical Analysis Methods   |  |
|----------|--|--|
|          | In order to check the statistical significance, 1-sided P-value for the log rank test will be        |  |
|          | calculated. 1-sided nominal type I error will be 5.89%. (the nominal alpha level is equal to the key |  |
|          | secondary at the final analysis, because we use a sequential procedure). The objective will be       |  |
|          | met if the 1-sided P-value calculated for the null hypothesis H0=[occurrence SSTI VE =0%] is         |  |
|          | lower than defined 1-sided alpha level.  |  |
| CCI      |  |  |
|          |  |  |
|          |  |  |
|          |  |  |
|          |  |  |
|          |  |  |
|          |  |  |
|          |  |  |
|          |  |  |
|          |  |  |
|          |  |  |
|          |  |  |
|          |  |  |
|          |  |  |
|          |  |  |
|          |  |  |
|          |  |  |
|          |  |  |

# 10.3.4. Immunogenicity analyses

The main analysis set for immunogenicity will be the mFAS.

| CCI |  |
|-----|--|
|     |  |
|     |  |
|     |  |
|     |  |
|     |  |
|     |  |
|     |  |
|     |  |
|     |  |
|     |  |
|     |  |
|     |  |
|     |  |
|     |  |
|     |  |
|     |  |
|     |  |
|     |  |
|     |  |
|     |  |
|     |  |
|     |  |
|     |  |
|     |  |
|     |  |
|     |  |

# 10.3.5. Safety analyses

The primary analysis will be performed on the Solicited Safety and Unsolicited Safety sets.

| Endpoint | Statistical Analysis Methods   |
|----------|--|
| Primary  | Within groups assessment The event $05\%$ confidence intervals (Cir) of any calletted $0.5\%$ (see Let   |
|          | (Day 1-7) period will be tabulated per study group and for each dose and overall. The same calculations will be performed for solicited Aes rated as grade 3 and fever >40°C/104°F. The overall incidence, with exact 95% confidence intervals (Cis) of any unsolicited AE, unsolicited Aes by MedDRA system organ class and by preferred term during the 30-day (Day 1.20) follow up performed for solicited will be tabulated per study group and for each dose and overall. |
|          | and overall. The same calculations will be performed for unsolicited Aes rated as grade 3 and fever >40°C/104°F, for unsolicited Aes causally related to vaccination and for grade 3 unsolicited Aes causally related to vaccination.
The number and percentages of subjects who experienced at least one SAE or any pIMD during the entire study period (Groups 1-3 Day 1-366, Groups 4 and 5 Day 1-426) will be reported.   |
|          | normal laboratory ranges with the changes from the baseline values will be tabulated by time point for Group 1 to 4 and Group 5 Step 1.
Duration will be presented.   |
|          | The verbatim reports of unsolicited symptoms will be reviewed by a GSK physician and the
signs and symptoms will be coded according to the MedDRA Dictionary for Adverse Event
Terminology.
Serious adverse events and withdrawal due to adverse event(s) will be described in detail.  |
|          |  |
|          |  |
|          |  |
|          |  |
|          |  |
